9.1 Efficacy Assessments

Not applicable.

9.1.1 *Imaging Assessment for the Study*

At the sponsor's discretion, scans may be collected for review.

This is not applicable for this study.

9.2 Adverse Events

The definitions of an AE or SAE can be found in [Appendix 3](#).

AEs will be reported by the participant (or, when appropriate, by a caregiver, surrogate, or the participant's legally authorized representative).

The investigator and any designees are responsible for detecting, documenting, and reporting events that meet the definition of an AE or SAE and remain responsible for following up AEs that are serious, considered related to the study treatment or the study, or that caused the participant to discontinue before completing the study.

Contacts for SAE reporting are specified in [Appendix 3](#)

9.2.1 *Time Period and Frequency for Collecting AE and SAE Information*

[Appendix 1](#) in the IB (BMS-986141) and Section 4.8 in the Summary of Product Characteristics (aspirin and ticagrelor) represent the Reference Safety Information, and they are used to determine expectedness of SAEs for expedited reporting.

All SAEs must be collected from the time of signing the consent, including those thought to be associated with protocol-specified procedures and within 30 days of discontinuation of dosing.

The investigator must report any SAE that occurs after these time periods and that is believed to be related to study drug or protocol-specified procedure, (eg, a follow-up skin biopsy).

- Medical occurrences that begin before the start of study treatment but after obtaining informed consent will be recorded on the appropriate section of the CRF module.
- All SAEs will be recorded and reported to Sponsor or designee within 24 hours, as indicated in [Appendix 3](#).
- The investigator will submit any updated SAE data to the sponsor or designee within 24 hours of updated information being available.

Investigators are not obligated to actively seek AEs or SAEs in former study participants. However, if the investigator learns of any SAE, including a death, at any time after a participant has been discharged from the study, and he/she considers the event reasonably related to the study treatment or study participation, the investigator must promptly notify the sponsor.

The method of evaluating and assessing causality of AEs and SAEs and the procedures for completing and reporting/transmitting SAE reports are provided in [Appendix 3](#).

9.2.2 Method of Detecting AEs and SAEs

Adverse events can be spontaneously reported or elicited during open-ended questioning, examination, or evaluation of a participant. Care should be taken not to introduce bias when collecting AE and/or SAEs. Inquiry about specific AEs should be guided by clinical judgement in the context of known AEs, when appropriate for the program or protocol.

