Table 2-2: On Treatment Procedural Outline (CV006037) - Treatment Arms 1, 2, and 3

Procedure	Day 1 (Visit 1)	Day 2 (Visit 2/Clinic Discharge ^a)	Day 8/ Study Discharge	Notes
Electrocardiogram	X	X		See note in screening procedures. Electrocardiograms will be collected at check-in, and 2 and 24 hours after BMS-986141 dosing. The 2-hour and 24-hour ECGs should be performed prior to the Badimon Chamber run.
Clinical Laboratory Tests	X	X		See note in screening procedures and Section 9.4.4 . Laboratory tests will be collected at check-in, and 2 and 24 hours after BMS-986141 dosing.
Urine Drug Test	X			See note in screening procedures. Performed at check-in; results must be reviewed before BMS-986141 dosing on Day 1.
Pregnancy Test	X			Performed at check-in; results must be reviewed prior to BMS-986141 dosing on Day 1.
Concomitant Medication Use	X	X	X	
Monitor for Non-Serious Adverse Events	X	X	X	
Monitor for Serious Adverse Events	X	X	X	See note in screening procedures.
Follow-up Telephone Call			X	±2 days. The scheduled follow-up telephone call will include review of the specific follow-up instructions and clinically pertinent re-assessment regarding those recommendations which are being provided to the participant to resume any prior medications, including, but not limited to, specific anti-platelet therapeutics.
PK Assessments				
Serial Blood PK Sampling	X	X		See Table 9.5-1 , Table 9.5-2 , and Table 9.5-3 .
Thrombosis Chamber Procedure	X	X		See Section 9.8 .

Table 2-2: On Treatment Procedural Outline (CV006037) - Treatment Arms 1, 2, and 3

Procedure	Day 1 (Visit 1)	Day 2 (Visit 2/Clinic Discharge ^a)	Day 8/ Study Discharge	Notes
				Each participant will undergo a total of 3 thrombosis chamber procedures.
Biomarker Assessments				See Section 9.8 .
[REDACTED]	X	X		[REDACTED]
[REDACTED]	X			[REDACTED]
Serum collection for SARS-CoV-2 serology	X			See Table 9.8-1 . Serum collected to be used for measurements of anti-SARS-CoV-2 serology.
Clinical Drug Supplies				
Ticagrelor BID or Aspirin, or Ticagrelor BID + Aspirin Administration	X	X		Those sourced by the investigator.
BMS-986141 Administration	X			Those supplied by BMS.

^a Evaluations performed prior to study discharge, or for participants who are prematurely discontinued.

Abbreviations: ADME = absorption, distribution, metabolism, and elimination; BID = twice daily; DNA = deoxyribonucleic acid; PD = pharmacodynamic; PK = pharmacokinetic

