3.3 Benefit/Risk Assessment

Participants will receive no known health benefit from participating in the study beyond that of an assessment of their overall health status.

BMS-986141 is a highly selective antagonist of PAR4, a thrombin-activated receptor found on human platelets. In animals, BMS-986141 has shown to block thrombosis with minimal increased in bleeding, even when combined with aspirin.²⁶

BMS-986141 has a safe and well tolerated profile in over 100 healthy volunteers across 5 Phase 1 studies using a wide dose range in single and multiple doses. The clinical pharmacology profile complements the mechanism of action and optimizes the benefit/risk ratio compared to other antiplatelet agents that have some disadvantages (eg, irreversible, pro-drug).

The impact of BMS-986141 influencing the exposures of ticagrelor or aspirin (and its major metabolite salicylic acid), is based on the nonclinical evaluation of drug interaction potential as a perpetrator. Exposures of BMS-986141 are expected to stay within the range of exposures that have been found to be safe in the single and multiple dose studies. The doses of ticagrelor and aspirin used in this study have been used in other drug-drug interaction studies and have an acceptable safety profile.

BMS-986141 is not expected to have an impact on the PD (platelet aggregation) of ticagrelor, aspirin, or its major metabolite, salicylic acid based on the mechanism of action, preclinical data of PAR4 antagonists, and data from the Phase 1 studies.

There is a small risk of increased bleeding in the dual therapy and triple therapy treatment arms; however, based on accumulated data of previous studies, no major bleeding events using BMS-986141 alone have been observed. Participants who do not currently receive any antiplatelet therapy, or who are currently on aspirin alone as their standard of care, will be excluded from Treatment Arm 3 (triple therapy).

Risks from the phlebotomy and perfusion chamber procedures are standard and include infection, bleeding, bruising, blood clot formation, discomfort at the phlebotomy site, and fainting.

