7.2 Method of Treatment Assignment

Study treatment will be dispensed at the study visits as listed in Schedule of Activities ([Section 2](#)).

Treatment arms will not be randomized but instead be allocated as open-label at the discretion of the Principal Investigator as detailed in [Section 5.1](#).

Enrolled participants, including those not dosed, will be assigned sequential participant numbers starting with 00001 (eg, 00001, 00002, 00003.... 00010). Those enrolled participants meeting inclusion and exclusion criteria will be eligible to be dosed.

Participants will not be replaced if they are discontinued from the study secondary to an AE unless the AE can be determined to be unrelated to treatment. If a participant is replaced after dosing then the replacement participant will be assigned the original participant's number plus 100. The replacement participant will receive the same treatment as the participant being replaced, but a new participant number will be assigned to him or her. For example, participant 00004 would be replaced by Participant 00104.

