7.3 Blinding

This is an open-label study; blinding procedures are not applicable.

Aortic strip analysis will be performed blinded. Aortic strips will be assigned and stored with a unique sample number unrelated to the participant number. Aortic strips will be processed by the histology department, who are blinded to the study entirely, and analyzed at a later date by an operator blinded to the aortic strip linked sample numbers.

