10.3.2 Safety Analyses

All safety analyses will be performed on the Treated Population.

Endpoint	Statistical Analysis Methods
Secondary: AEs, clinical laboratory	Descriptive summaries will be presented for continuous variables using number of participants (N), mean, standard deviation, median, minimum, and maximum. Descriptive summaries for categorical variables will utilize counts

values, vital signs, ECGs, or other safety biomarkers	and percentages. All recorded AEs will be listed and tabulated by system organ class, preferred term, treatment arm, and treatment. Vital signs, ECGs, and clinical laboratory test results will be listed and summarized by planned time point, treatment arm, and treatment. Marked abnormal clinical laboratory test results will be summarized by treatment arm and treatment. Any significant physical examination findings will be listed. Electrocardiogram readings will be summarized by planned time point, treatment arm, and treatment, and investigator-identified abnormalities, if present, will be listed.
---	--

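### Questions about specific adverse events are left to clinical judgement in an open-label trial, so minor bleeding may be asked about unevenly across arms and treatments

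*Combined protocol and SAP*

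**What the plan says.** **How AEs are found.** Section 9.2.2 gives the routine: "Adverse events can be spontaneously reported or elicited during open-ended questioning, examination, or evaluation of a participant". It adds a general caution, "Care should be taken not to introduce bias when collecting AE and/or SAEs", with no procedure attached. It then leaves targeted questions to staff: "Inquiry about specific AEs should be guided by clinical judgement in the context of known AEs, when appropriate for the program or protocol".

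**What staff know.** Section 7.3: "This is an open-label study; blinding procedures are not applicable". Only the aortic strip analysis is blinded. Section 7.2: "Treatment arms will not be randomized but instead be allocated as open-label at the discretion of the Principal Investigator".

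**What staff are told about bleeding.** Section 3.3: "There is a small risk of increased bleeding in the dual therapy and triple therapy treatment arms". The same sentence says that no major bleeding has been seen with BMS-986141 alone. Section 3.3 also lists bleeding and bruising among the risks of phlebotomy and the perfusion chamber, and says that ticagrelor and aspirin can themselves increase bleeding.

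**What is fixed for everyone.** For laboratory tests, Table 2-2 says: "Laboratory tests will be collected at check-in, and 2 and 24 hours after BMS-986141 dosing". Table 2-3 sets the same times for Arm 4. Section 9.4.4 includes hemoglobin, hematocrit and urine blood. Physical examination is scheduled on Days 1 and 2, and AE monitoring is marked on Days 1, 2 and 8. The notes on the Day 8 call mention follow-up instructions and the resumption of earlier medication, and no bleeding question.

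**How AEs are reported.** Section 10.3.2: "All recorded AEs will be listed and tabulated by system organ class, preferred term, treatment arm, and treatment". No test and no bleeding endpoint is planned.

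**The concern.** Section 9.2 has AEs reported by the participant, so a nosebleed or a bruise that leaves no laboratory trace reaches the record through what the participant volunteers, what is asked and what an examination shows. When staff know the treatment and may choose when to ask, the amount of asking can vary with arm, with time since dosing or with the individual interviewer. Differences in recorded counts could then come from the questioning and not from the drugs.

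At stake are the secondary objectives in Table 4-1. They describe safety separately for background therapy, for background plus BMS-986141, and for BMS-986141 alone. Low bleeding is central to the rationale for the drug in Section 3.2, so readers will look at the bleeding lines of the AE tables even though no formal comparison is planned.

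**Working it through.** **1. Is there a figure to reproduce?** The plan gives no bleeding rate and no probability that a bleed is recorded. Its only precision figures (Section 10.1) concern log thrombus area. They reproduce as t(0.975, n−1) × 0.263/√n: 0.146 for n = 15 and 0.188 for n = 10. They have no bearing on this point.

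**2. Which contacts have a standard way of finding bleeding, the same in all arms?** (Tables 2-2 and 2-3, Sections 6.2 and 9.4.4)

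| Contact | Fixed and equal in all arms | Standard bleeding question in the protocol |
|---|---|---|
| Day 1 check-in | Laboratory tests, examination (or one done at screening within 24 hours of dosing), eligibility check | In effect yes: exclusion 1(d) covers current or recent bleeding and names epistaxis, gastrointestinal and urogenital sites |
| Day 1, 2 hours, then release | Laboratory tests, AE monitoring | None |
| Day 2, 24 hours | Laboratory tests, examination, AE monitoring | None |
| Day 8 (±2 days), telephone | AE monitoring | None |

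The last row is the weakest. No sample or examination is scheduled after Day 2, and the call is the only scheduled contact. Drug exposure is not over by then: Section 6.1 and Appendix 4 put five half-lives of BMS-986141 at 9 days and Section 9.2.5 at 5 days. Either figure runs well past the Day 2 visit.

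**3. Which bleeding is exposed?** Bleeding with a fall in hemoglobin, a transfusion or treatment is addressed by the discontinuation criteria (Section 8.1) and the stopping rules (Section 8.1.2), which apply to all arms, and by laboratory tests through Day 2. SAEs are collected in all arms for 30 days. What remains is mainly minor bleeding that only the participant can report.

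**4. Illustration of size, on assumptions only.** Assume the same true risk p in every arm, a probability of being recorded of 0.9 if asked, and of 0.5 to 0.7 if only volunteered. Take the extreme in which everyone in a 15-participant arm is asked and nobody in Arm 4 (10 participants) is.

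- Apparent ratio = (p × 0.9)/(p × s), where s is the probability of being recorded in Arm 4. The risk p cancels.
- s = 0.9 (equal asking): 1.00. s = 0.7: 0.9/0.7 = 1.29. s = 0.5: 0.9/0.5 = 1.80.
- Expected counts at p = 20%: 15 × 0.20 × 0.9 = 2.7 of 15, against 10 × 0.20 × 0.7 = 1.4 or 10 × 0.20 × 0.5 = 1.0 of 10. As rates, 18% against 14% or 10%.
- At p = 10% and s = 0.5: 9% against 5%. At p = 30% and s = 0.5: 27% against 15%.

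These ratios are only the assumed probabilities divided by each other. Partial unevenness gives something between 1.00 and the extreme, and asking more in Arm 4 would reverse the direction.

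**5. Against chance.** Exact 95% limits are 4% to 48% for 3 of 15 and 3% to 56% for 2 of 10. With no events, the upper limits are 22% (n = 15) and 31% (n = 10). Random error is larger than the illustrated bias.

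**The case against.** A reader might infer that bleeding *is* asked about unevenly, with more questions in Arms 1 to 3 and fewer in Arm 4 and before BMS-986141, so that the counts reflect who was asked. The documents do not support that.

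- Section 9.2.2 governs inquiry about specific events. It does not tell staff to choose participants by arm, and it tells them to avoid bias. It permits uneven asking without requiring it.
- The direction is open. Every participant has three chamber runs, a procedure whose stated risks include bleeding and bruising, and bleeding is a known effect of the background drugs alone. Judgement based on known AEs could lead staff to ask in every arm and period.
- Section 3.3 names a small risk, which is weaker than expecting bleeding.
- It would be wrong to say that no visit covers bleeding in a standard way, because exclusion 1(d) is checked on Day 1 in all arms.
- The CRF and any call script are not among the documents and may already contain such a question.
- Safety is secondary and descriptive, the arms are not randomized, Arm 4 is a healthy population, and the counts are very imprecise.

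All of this stands, and it limits the point to a possible bias in minor bleeding counts. It does not remove the point. After dosing, the protocol specifies no standard bleeding question, and the caution against bias has no procedure behind it. Small arms do not excuse a systematic error that can be avoided at almost no cost.

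**Conclusion.** The concern holds as a risk. Discretionary questioning by unblinded staff, with arm-specific bleeding expectations written into the protocol, could bias counts of minor, participant-reported bleeding by arm and treatment, chiefly between Day 2 and Day 8. Neither the occurrence nor the direction of such a bias can be read from the documents, and its size cannot be estimated from them. The 1.3 to 1.8 range rests wholly on the assumed recording probabilities and on complete separation of asked and unasked groups. The primary endpoint and the sample size are untouched. This is a modest improvement, worth making because it is cheap.

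**What to change.** In Section 9.2.2, add one bleeding question set covering epistaxis, gastrointestinal bleeding, urogenital bleeding, and bleeding or bruising at the puncture site. Ask it in identical words of every participant in all four arms, at contacts already scheduled:

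- Day 1 check-in, alongside the exclusion 1(d) check, which also gives a baseline;
- before release on Day 1;
- Day 2;
- the Day 8 call, with the question added to the call notes in Tables 2-2 and 2-3.

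Record yes or no for each site. Keep open-ended questioning for all other AEs. If the CRF or a call script already holds such a question, cite it in Section 9.2.2.

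**Cost.** One CRF item and a call script, with no added visit, procedure or staff. More minor bleeds and puncture-site bruises will be recorded, so Section 10.3.2 should tabulate these separately from other bleeding.

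**What it leaves open.** Participants still know their treatment, so what they choose to report may differ. The change does not touch three other limits on these tables: non-serious AEs before Day 1 are collected only from run-in participants (Table 2-1), the background-alone window on Day 1 is about 2 hours (Section 5.1), and the contrast with healthy Arm 4 is not randomized.

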9.2.3 Follow-up of AEs and SAEs

- Nonserious AEs should be followed to resolution or stabilization, or reported as SAEs if they become serious (see [Appendix 3](#)).
- Follow-up is also required for nonserious AEs that cause interruption or discontinuation of study treatment and for those present at the end of study treatment as appropriate.
- All identified nonserious AEs must be recorded and described on the nonserious AE page of the CRF (paper or electronic). Completion of supplemental CRFs may be requested for AEs and/or laboratory abnormalities that are reported/identified during the course of the study.

All SAEs will be followed until resolution, until the condition stabilizes, until the event is otherwise explained, or until the participant is lost to follow-up (as defined in [Section 8.3](#)).

Further information on follow-up procedures is given in [Appendix 3](#).

9.2.4 Regulatory Reporting Requirements for SAEs

- Prompt notification by the investigator to the Sponsor of SAEs is essential so that legal obligations and ethical responsibilities towards the safety of participants and the safety of a product under clinical investigation are met.
- An investigator who receives an investigator safety report describing SAEs or other specific safety information (eg, summary or listing of SAEs) from the Sponsor will file it along with the Investigator's Brochure and will notify the IRB/IEC, if appropriate according to local requirements.

Sponsor or designee will be reporting adverse events to regulatory authorities and ethics committees according to local applicable laws including European Directive 2001/20/EC and FDA Code of Federal Regulations 21 CFR Parts 312 and 320. A SUSAR (Suspected, Unexpected Serious Adverse Reaction) is a subset of SAEs and will be reported to the appropriate regulatory authorities and investigators following local and global guidelines and requirements.

9.2.5 *Pregnancy*

If, following initiation of the study treatment, it is subsequently discovered that a participant is pregnant or may have been pregnant at the time of study exposure, including during at least for 5 half-lives (5 days) plus 30 days (duration of ovulatory cycle), for a total of 35 days after study product administration, the investigator must immediately notify the BMS Medical Monitor/designee of this event and complete and forward a Pregnancy Surveillance Form to BMS Designee within 24 hours of awareness of the event and in accordance with SAE reporting procedures described in [Appendix 3](#).

If the investigator determines a possible favorable benefit/risk ratio that warrants continuation of study treatment, or re-initiation of study treatment, a discussion between the investigator and the BMS Medical Monitor/designee must occur.

Follow-up information regarding the course of the pregnancy, including perinatal and neonatal outcome and, where applicable, offspring information, must be reported on the Pregnancy Surveillance Form.

Any pregnancy that occurs in a female partner of a male study participant should be reported to Sponsor or designee. In order for Sponsor or designee to collect any pregnancy surveillance information from the female partner, the female partner must sign an informed consent form for disclosure of this information. Information on this pregnancy will be collected on the Pregnancy Surveillance Form.

9.2.6 *Laboratory Test Result Abnormalities*

The following laboratory test result abnormalities should be captured on the nonserious AE CRF page or SAE Report Form electronic, as appropriate. Paper forms are only intended as a back-up option when the electronic system is not functioning.

- Any laboratory test result that is clinically significant or meets the definition of an SAE
- Any laboratory test result abnormality that required the participant to have study treatment discontinued or interrupted
- Any laboratory test result abnormality that required the participant to receive specific corrective therapy

It is expected that wherever possible, the clinical rather than laboratory term would be used by the reporting investigator (eg, anemia versus low hemoglobin value).

9.2.7 *Potential Drug Induced Liver Injury (DILI)*

Wherever possible, timely confirmation of initial liver-related laboratory abnormalities should occur prior to the reporting of a potential DILI event. All occurrences of potential DILIs, meeting the defined criteria, must be reported as SAEs (see [Section 9.2](#) and [Appendix 3](#) for reporting details).

Potential DILI is defined as:

1) ALT or AST elevation $> 3 \times$ ULN

AND

2) Total bilirubin $> 2 \times$ ULN, without initial findings of cholestasis (elevated serum alkaline phosphatase),

AND

3) No other immediately apparent possible causes of aminotransferase elevation and hyperbilirubinemia, including, but not limited to, viral hepatitis, pre-existing chronic or acute liver disease, or the administration of other drug(s) known to be hepatotoxic.

9.2.8 *Other Safety Considerations*

Any significant worsening noted during interim or final physical examinations, ECG, x-ray filming, any other potential safety assessment required or not required by protocol should also be recorded as a nonserious or SAE, as appropriate, and reported accordingly.

9.3 *Overdose*

For this study, any dose of BMS-986141 greater than 4 mg and any dose of aspirin greater than 75 mg within a 24-hour time period will be considered an overdose. As the standard of care for ticagrelor is 90 mg given BID, any dose of ticagrelor greater than 180 mg within a 24-hour time period will be considered an overdose.

9.4 *Safety*

Planned time points for all safety assessments are listed in the Schedule of Activities ([Section 2](#)).

9.4.1 *Physical Examinations*

Refer to Schedule of Activities (Section 2).

9.4.1.1 *Medical Photography*

Starting on Day 1, standard baseline photographs of any area with clinical findings will be taken at the discretion of the Principle Investigator. If there are any changes with the affected areas or new clinical findings, additional photographs will be obtained. Photographs will not be needed if there is no clinical finding or no change in the affected areas.

9.4.2 *Vital signs*

Refer to Schedule of Activities (Section 2).

9.4.3 *Electrocardiograms*

Refer to Schedule of Activities ([Section 2](#)).

9.4.4 *Clinical Safety Laboratory Assessments*

- Investigators must document their review of each laboratory safety report.
- A local laboratory will perform the analyses and will provide reference ranges for these tests.
- Results of clinical laboratory tests performed on Day 1 must be available prior to BMS-986141 dosing.

Hematology	
Red blood cells	
Hemoglobin	
Hematocrit	
Total leukocyte count, including differential	
Platelet count	
Chemistry	
AST	Total protein
ALT	Albumin
Total bilirubin	Sodium
Direct bilirubin	Potassium
Alkaline phosphatase	Chloride
Lactate dehydrogenase	Calcium
Creatinine	Phosphorus
Blood urea nitrogen	Magnesium
Uric acid	Creatine kinase
Fasting glucose	
Coagulation	
INR	
aPTT	
Prothrombin time	
Platelet count	
Urinalysis	
Protein	
Glucose	
Blood	
Leukocyte esterase	
Specific gravity	
pH	
Microscopic examination of the sediment if blood, protein or leukocytes esterase are positive on the dipstick	
Serology	

Serum for hepatitis C antibody, hepatitis B surface antigen, HIV-1 and -2 antibodies (screening only). See [Appendix 7](#) for hepatitis B serologic test results interpretation.

Other Analyses

Test for drugs of abuse and alcohol (urine or serum) (screening and Day 1)

Pregnancy test (WOCBP only: screening, predose, clinic discharge)

Follicle-stimulating hormone (postmenopausal women only; screening)

